3.3.3 Handling of Unscheduled Visits

Unscheduled, retest (same visit number assigned), and early discontinuation measurements will contribute to the summaries. Visits for visit-based data will follow a windowing convention as described in Section 3.3.2. If there are multiple observations collected at the same date and time, unscheduled visit record will be considered last.

Listings will include scheduled, unscheduled, retest and early discontinuation data.

3.3.4 Multiplicity/Multiple Comparisons

The primary objective of the study is to assess the safety and tolerability of AZD7442. No statistical hypotheses will be tested.

3.3.5 Handling of Protocol Deviations in Study Analysis

A detailed list of possible Important Protocol Deviations (IPDs), and the process for reviewing them by the Clinical Study Team is discussed in the most recent version of the IQVIA Protocol Deviation Management Plan (PDMP).

The following categories of protocol deviations will be reviewed by the medical and statistical team members prior to Clinical Database Lock:

- Deviations relating to informed consent and process, inclusion and exclusion criteria
- Participants who fail to completely or correctly have a required laboratory assessment performed

- Participants who experience deviations related to planned study procedures and safety
- Participants who receive concomitant use of restricted medications per CSP Section 6.5
- Participants who experience an investigational product deviation
- Deviations from the responsibility of the principal investigator
- Deviations relating to improper source documents and management of the documents
- Deviations relating to regulatory requirement
- Deviations relating to facilities/equipment

4 STATISTICAL ANALYSIS

This section provides information on definitions, derivation, and analysis/data presentation by domain.

4.1 Study Population

The domain study population covers participant disposition, analysis sets, protocol deviations, demographics and baseline characteristics, disease characteristics, medical history, prior and concomitant medication, and study drug compliance.

4.1.1 Subject Disposition and Completion Status

4.1.1.1 Definitions and Derivations

Treatment groups are reported based on randomized treatment. The Enrolled Participant Analysis Set as defined in Section 3.2 is used for reporting disposition and screening failures. Disposition information can be directly obtained from the eCRF.

4.1.1.2 Presentation

The disposition table of participants will include the number of participants with informed consent, and screen failure. Numbers and percentages will be presented by treatment and total for the following. Note: Percentages are based on total randomized participants.

- Randomized participants
- Participants randomized but not dosed
- Participants who completed the end of treatment visit
- Participants who discontinued early from treatment
 - Reason for discontinuing early from treatment

- Participants who completed the study
- Participant who discontinued early from study
 - Reason for discontinuing early from study

4.1.2 Analysis Sets

4.1.2.1 Definitions and Derivations

Analysis sets are defined in Section [3.2](#).

4.1.2.2 Presentation

Number of participants will be reported by treatment for Full Analysis Set (FAS), Safety Analysis Set, PK Analysis Set, NLF PK Analysis Set, ADA evaluable analysis set (separated by ADA of AZD8895, ADA of AZD1061, and ADA of AZD7442), and nAb evaluable analysis sets (Pseudovirus, Authentic virus). For each analysis set, number of participants excluded and number for each reason will be reported by treatment.

4.1.3 Protocol Deviations

4.1.3.1 Definitions and Derivations

Protocol deviations (IPDs) are identified in the most recent version of the protocol deviation management plan for the following categories:

- Deviations related to informed consent and process
- Deviations from inclusionary criteria
- Deviations from exclusionary criteria
- Deviations related to laboratory assessments
- Restricted medication taken per CSP Section 6.5
- Deviations related to study procedures
- Deviations impacting safety
- IMP deviations
- Deviations related to principal investigator responsibility
- Deviations to source documentation
- Deviations to regulatory compliance
- Deviations to facilities/equipment

4.1.3.2 Presentation

Number and percentage of participants with IPDs will be provided by treatment group and total for each category of protocol deviations. The summary will be based on the Safety Analysis Set.

4.1.4 Demographics

4.1.4.1 Definitions and Derivations

Demographics are categorized as follows:

- Age group:
 - ≥ 12 to < 18 years, ≥ 18 to < 65 years, ≥ 65 to < 75 years, ≥ 75 to < 80 years and ≥ 80 years.
- Sex: Male, Female
- Ethnicity: Hispanic or Latino, Not Hispanic or Latino
- Race: American Indian or Alaska Native, Asian, Black or African American, Native Hawaiian or Other Pacific Islanders, White

4.1.4.2 Presentation

The summary of demographics characteristics will be provided for the Safety Analysis Set, summarized by actual treatment groups. Other analysis sets will be summarized if deemed necessary.

Demographics will be summarized by treatment group and total using descriptive statistics for age and number and percentage of participants for age group, sex, race, and ethnicity.

4.1.5 Baseline Characteristics

4.1.5.1 Definitions and Derivations

Baseline characteristics include the following:

- Weight (kg)
- Height (cm)
- Body Mass Index (BMI) (kg/m^2) = $\text{weight (kg)} / [\text{height (m)}^2]$ as a continuous variable
- BMI as a categorical variable (< 25 , $25 - < 30$, $30 - < 35$, ≥ 35)
- Smoking History (Current, Former, Never); average pack-year for Current/Former smokers
- Screening result from NP swab for SARS-CoV-2 RT-PCR (Positive, Negative)

- Previous COVID-19 vaccination status (Vaccinated [within 3 months prior to first IMP dose], Not Vaccinated [or latest vaccination more than 3 months prior to first IMP dose])
- Time since previous COVID-19 vaccination (days) calculated as (Date of first IMP Dose) - (Date of latest COVID-19 vaccination prior to first IMP dose) + 1

Partial dates for latest COVID-19 vaccination prior to first IMP dose will be imputed as follows:

- If year and month are available and day is missing, then impute at the last day for the respective month. If this results in a date that is after first IMP dose, then set to the day prior to first IMP dose.
- If year is available and month and day are missing, then impute as missing. In this case, previous COVID-19 vaccination status and time since previous COVID-19 vaccination (days) will also be missing.

4.1.5.2 Presentation

Baseline characteristics will be summarized with demographics, as specified in Section [4.1.4.2](#).

4.1.6 Disease Characteristics

4.1.6.1 Definitions and Derivations

Disease characteristics include the following at baseline:

- Active treatment for solid tumor and hematologic malignancies (Yes/No);
- Receipt of solid-organ transplant and taking immunosuppressive therapy (Yes/No);
- Receipt of chimeric antigen receptor T-cell or hematopoietic stem cell transplant; moderate or severe primary immunodeficiency (Yes/No);
- Moderate or severe primary immunodeficiency (Yes/No);
- Advanced or untreated HIV infection (Yes/No);
- Active treatment with systemic high-dose corticosteroids, alkylating agents, antimetabolites, tumor necrosis factor blockers and other biologic agents that are immunosuppressive or immunomodulatory (Yes/No);
- Serum for SARS-CoV-2 Serology (Positive, Negative);
- Other (Yes/No)

4.1.6.2 Presentation

Disease characteristics will be summarized by treatment group and total using descriptive statistics for continuous variables and number and percentage of participants for categorical variables.

Summary of disease characteristics will be provided for the Safety Analysis Set, presented with actual treatment groups.

4.1.7 Medical History and Concomitant Disease

4.1.7.1 Definitions and Derivations

Medical/surgical history and concomitant disease will be coded using Medical Dictionary for Regulatory Activities (MedDRA) 26.0 or higher.

Medical/surgical history are defined as any medical or surgical or condition/disease that started and stopped before the first dose of IMP. Concomitant diseases are defined as any medical condition/disease that started before the first dose of IMP and were ongoing at the time of the dose of IMP or ended on date of dose.

4.1.7.2 Presentation

Medical and surgical history and concomitant disease will be summarized by System Organ Class (SOC) and Preferred Term (PT) by actual treatment groups and total for participants in the Safety Analysis Set.

A participant having more than one condition/disease within the same SOC or PT will be counted only once for that SOC or PT.

4.1.8 Prior and Concomitant Medications

4.1.8.1 Definitions and Derivations

All medications will be coded using the World Health Organization (WHO) Drug Global dictionary, version B3 March 2023 or a more recent version.

A medication will be regarded as prior if it was stopped prior to the first dose of IMP. A medication will be regarded as concomitant if the start date is on or after the date of the first dose of IMP, or if it started on or prior to the first dose of IMP and ongoing after the dose of IMP.

The handling of partial/missing dates is detailed in Appendix [A 1](#).

4.1.8.2 Presentation

Prior and concomitant medications will be summarized by Anatomical Therapeutic Class (ATC) Level 4 and preferred drug name by treatment and total based on the Safety Analysis

Set. A participant having more than one medication within the same ATC Level 4 or preferred drug name will be counted only once for that ATC Level 4 or preferred drug name.

4.1.9 Study Drug Compliance

4.1.9.1 Definitions and Derivations

Treatment compliance will be calculated as follows:

$$\text{Treatment compliance (\%)} = (\text{Total number of actual dosing occasions} / \text{total number of expected dosing occasions}) \times 100\%$$

Treatment compliance is categorized as: $\leq 80\%$, $> 80\%$ to $\leq 100\%$, $> 100\%$ to $\leq 120\%$, $> 120\%$.

In order to allow for participants who discontinue IMP early in the compliance calculation, the number of expected dosing occasions will be calculated as the number of scheduled dosing visits up to and including the last available dosing visit for that participant.

4.1.9.2 Presentation

Treatment compliance, and total number of dosing occasions will be summarized by treatment group, using descriptive statistics for participants in the Safety Analysis Set. Additionally, the categorical summary of treatment compliance defined in Section 4.1.9.1 will be shown.

4.2 Endpoint Analyses

This section covers details related to the endpoint analyses such as primary, secondary, other endpoints.

Statistical category	Endpoint	Population	Intercurrent event strategy	Population level summary (analysis)	Details in section
Objective 1: To evaluate the safety, and tolerability of AZD7442 in adult and pediatric participant ≥ 12 years of age.					
Primary	Incidence and exposure adjusted incidence of AEs, SAEs, and AESIs	Safety analysis set	N/A	Descriptive	Section 4.3.2
Objective 2: To evaluate the immunogenicity of AZD7442 in adult and pediatric participant ≥ 12 years of age.					
Primary	Incidence of ADA to AZD7442	ADA evaluable analysis set	N/A	Descriptive	Section 4.2.1
Objective 3: To evaluate the PK of AZD7442 in adult and pediatric participant ≥ 12 years of age.					

Secondary	Serum AZD7442 (tixagevimab and cilgavimab) concentrations PK parameters	PK analysis set	N/A	Descriptive	Section 4.2.24.2.1
Objective 4: To determine anti-SARS-CoV-2 nAb levels in serum after administration of AZD7442 in adult and pediatric participant ≥ 12 years of age.					
Secondary	Changes from baseline in GMTs and GMFRs values in SARS-CoV-2 nAbs (wild-type assay or pseudo neutralization assay)	nAb evaluable analysis sets	N/A	Descriptive	Section 4.2.2
Objective 5: Exploratory – See Section 4.2.3					

4.2.1 Primary Endpoints – Immunogenicity

This section describes immunogenicity derivations and analyses. The definitions, and presentation of adverse events are given in Section 4.3.2.

4.2.1.1 Definition

ADA assessments of serum samples will be conducted utilizing a tiered approach (screen, confirm, titer), and ADA data will be collected at scheduled visits shown in Protocol Section 1.3. ADA results from each sample will be reported as either positive or negative. If the sample is positive, the ADA titer will be reported as well. In addition, the presence of neutralizing ADA may be tested for all ADA-positive samples. The neutralizing ADA results will be reported as positive or negative. A participant is defined as being ADA-positive if the participant is ADA evaluable and a positive ADA result is available at any time, including baseline and all post-baseline measurements; otherwise, the participant is defined as ADA negative.

4.2.1.2 Derivations

The number and percentage of ADA-evaluable participants in the following ADA categories in each treatment group will be determined. The number of ADA-evaluable participants in the treatment group will be used as the denominator for percentage calculation. Note that, ADA responses will be summarized for AZD8895, AZD1061, and AZD7442 separately.

- ADA positive at any visit (at baseline and/or post-baseline). AZD7442 is ADA positive if either AZD8895 or AZD1061 is ADA positive. The percentage of these participants in a population is known as ADA prevalence.
- Treatment-induced ADA positive (ADA negative at baseline and ADA positive at ≥ 1 post-baseline assessment with ADA titer $\geq 2 \times$ MRD [minimum required dilution]). In a situation that one of the components AZD8895 and AZD1061 is treatment-induced ADA positive, and the other component is treatment-boosted

ADA positive (as defined below), AZD7442 will be counted in the worst case (i.e., treatment-induced ADA positive).

- Treatment-boosted ADA positive (baseline ADA titer that was boosted by ≥ 4 -fold following drug administration). AZD7442 is treatment-boosted ADA positive if either AZD8895 or AZD1061 is treatment-boosted ADA positive, except in the situation described in the treatment-induced bullet above.
- Treatment-emergent ADA positive (either treatment-induced ADA positive or treatment-boosted ADA positive). The percentage of these participants in a population is known as ADA incidence.
- ADA positive post-baseline and positive at baseline.
- ADA positive at baseline and not detected post-baseline.
- Treatment-emergent ADA (TE-ADA) persistently positive for AZD8895 and AZD1061, is defined as treatment-emergent ADA positive participants having at least 2 post-baseline ADA positive measurements with titer $\geq 2 \times \text{MRD}$ at least 16 weeks (112 days) between the first and last positive measurement, or an ADA positive result at the last available assessment. AZD7442 is persistently positive if one of AZD8895 and AZD1061 is persistently positive.
- Treatment-emergent ADA (TE-ADA) transiently positive for AZD8895 and AZD1061, is defined as treatment-emergent ADA positive participants having at least one post-baseline ADA positive measurement with titer $\geq 2 \times \text{MRD}$ and not fulfilling the conditions for TE-ADA persistently positive. AZD7442 is transiently positive if the participant is treatment-emergent ADA positive, but neither AZD8895 nor AZD1061 is not fulfilling persistently positive ADA response.
- Non-treatment emergent ADA positive, defined as participants being ADA positive and not fulfilling the conditions for TE-ADA positive.

In addition, the following ADA category may be summarized.

- Neutralizing ADA (to AZD8895, AZD1061, or AZD7442) positive at any time.

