1.3 Sample Size

Approximately 200 participants will be randomized to study intervention: 100 participants to Arm A (AZD7442 600 mg IM on Day 1 then 300 mg IM Q3M for 12 months) and 100 participants to Arm B (AZD7442 1200 mg IV on Day 1 then 600 mg IM Q6M for 12 months).

If the true AE rate is 3%, the probability of observing at least one AE in 100 participants is 95%. The number of participants in the study would also allow for assessment of immunogenicity based on ADA prevalence observed in PROVENT (D8850C00002; NCT04625725).

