4.2.1.3 Primary Analysis of ADA

A summary of the number and percentage of participants who developed detectable ADA to AZD7442 (ADA results to AZD8895 and AZD1061 will be reported separately) by ADA categories (Section 4.2.1.2) in different treatment arms will be presented based on the ADA evaluable analysis set. ADA assessments collected post-dose on the days of IMP administration will be excluded. In addition, descriptive statistics of the maximum titer will

be presented by ADA category. ADA results and titers will be summarized by visit and treatment group.

ADA results will be listed for all participants in the Safety Analysis Set regardless of ADA-evaluable status. ADA titer will be presented, and neutralizing ADA data may be presented for samples confirmed positive for the presence of ADA to AZD7442. AEs in ADA positive participants by ADA positive category will be listed.

The effect of ADA on PK, and safety will be examined by descriptive summaries, if data allow. Descriptive summaries of PK concentration on participants in both the ADA evaluable analysis set and PK analysis set, number of participants having AEs in different categories, and number of participants with AEs by System Organ Class (SOC) and preferred term (PT) will be provided by ADA response: Treatment-emergent ADA positive, non-treatment emergent ADA positive, and ADA negative, and by treatment groups.

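### The SAP's rule for transient ADA to AZD7442 has a double negative and, read literally, selects participants whose two components are both persistently positive

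*SAP*

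**What the plan says.** SAP Section 4.2.1.2 lists the ADA categories to be reported separately for AZD8895, AZD1061 and the combination AZD7442. Three rules bear on this point.

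- **Persistent, combination level.** "AZD7442 is persistently positive if one of AZD8895 and AZD1061 is persistently positive".
- **Transient, component level.** A component is transient when the participant is treatment-emergent positive with at least one post-baseline positive of sufficient titer "and not fulfilling the conditions for TE-ADA persistently positive". This has a single negative.
- **Transient, combination level.** "AZD7442 is transiently positive if the participant is treatment-emergent ADA positive, but" "neither AZD8895 nor AZD1061 is not fulfilling persistently positive ADA response". This has two negatives.

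Section 4.2.1.3 then uses the categories. The counts and percentages by category "in different treatment arms will be presented based on the ADA evaluable analysis set". Maximum titer is also summarized by ADA category, and AEs in ADA-positive participants are listed by ADA-positive category. Nowhere else in the SAP or the protocol is the AZD7442 transient rule restated or corrected.

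**The concern.** Persistent and transient should divide the treatment-emergent participants into two groups that do not overlap and leave nobody out. The combination-level transient rule does the reverse of what its label says. It admits participants with two persistent components and shuts out those with none.

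Incidence of ADA is one of the two primary endpoints, and these categories are part of its planned presentation. Protocol Section 4.3 says the comparison of 3-month and 6-month dosing will show whether immunogenicity differs with frequency of administration, so persistence by arm bears on a stated aim. With literal coding, the transient row for the combined product would hold the wrong people, and the maximum titers shown there would be those of doubly persistent participants. SAP Sections 4.2.1.4 and 4.2.1.5 plan no sensitivity or supplementary analysis that might bring the error to light.

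**Working it through.** The documents attach no figure to this rule, so there is none to reproduce; the check is logical.

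**Inputs** (all from SAP Section 4.2.1.2): the three rules quoted above. I also assume that AZD7442 is treatment-emergent positive when at least one component is. This follows the pattern of the basic rule ("AZD7442 is ADA positive if either AZD8895 or AZD1061 is ADA positive") and of the treatment-boosted rule.

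**Step 1: the logic.** Let P1 and P2 mean that AZD8895 and AZD1061, respectively, are persistently positive.

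- As written: not(not P1) and not(not P2) = P1 and P2.
- Single-negative form: not P1 and not P2.

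**Step 2: all combinations.** Give each component one of three states: N (not treatment-emergent), T (treatment-emergent, not persistent) or P (treatment-emergent and persistent). That makes 3 × 3 = 9 pairs. N/N is not treatment-emergent, which leaves 8.

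| AZD8895 / AZD1061 | Pairs | Persistent rule | Transient, as written | Transient, single negative |
|---|---|---|---|---|
| N/T, T/N, T/T | 3 | no | no | yes |
| N/P, P/N, T/P, P/T | 4 | yes | no | no |
| P/P | 1 | yes | yes | no |

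As written, P/P is in both classes and three pairs are in neither. With the single negative, the classes hold 3 + 5 = 8 pairs, each once.

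**Step 3: the other reading of the persistent rule.** The table reads *one of* as at least one. If it meant exactly one, P/P would leave the persistent class and the overlap would go. P/P would still be labelled transient, and N/T, T/N and T/T would still be unclassified.

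**Step 4: effect on counts.** Let b, o and n be the numbers of treatment-emergent participants with both, one and no persistent component. The correct counts are b + o persistent and n transient. The literal counts are b + o persistent and b transient, with n unclassified. The transient count is therefore wrong by b − n.

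The documents give no ADA rates, so the following is an assumed illustration with 12 treatment-emergent participants, of whom o = 3:

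| b | n | Persistent | Transient, correct | Transient, as written | Unclassified |
|---|---|---|---|---|---|
| 0 | 9 | 3 | 9 | 0 | 9 |
| 4 | 5 | 7 | 5 | 4 | 5 |
| 9 | 0 | 12 | 0 | 9 | 0 |

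In the middle row the literal classes sum to 7 + 4 = 11, not 12, with 4 people counted twice and 5 missing. Under the exactly-one reading the same row gives 3 persistent, 4 transient and 5 unclassified. When b = n the literal total happens to equal the treatment-emergent total although the membership is wrong, so comparing totals alone can miss the error.

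**The case against.** The best reply is that this is a slip of drafting whose intent is plain. The component-level rule in the same bullet has one negative, the preceding bullet defines persistence for the combination, and the label itself says transient. A careful programmer would probably code what was meant.

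It can also be said that the reach is small. The SAP defines ADA incidence as the treatment-emergent percentage, which this sentence does not touch. The summaries of PK and AEs by ADA response use treatment-emergent, non-treatment-emergent and negative groups, not the persistent/transient split. No hypothesis is tested, and nothing in the documents turns on the split. Finally, the double counting depends on reading *one of* inclusively.

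Most of this stands, and it limits the consequence. It does not make the sentence right. A programmer who follows the intent departs from the signed text; one who follows the text produces a wrong row; two independent programmers may disagree. The inclusive reading is the natural one beside the neighbouring rules that use *either*, and the misclassification survives the alternative.

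**Conclusion.** The concern holds. As written, the AZD7442 transient rule selects only participants with both components persistently positive and omits every participant with none. If it is coded literally, all true transient cases are lost from the classification. All doubly persistent participants are also reported as transient, and on the inclusive reading of the persistent rule they are counted in both classes. The actual number affected cannot be sized from the documents.

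This should be corrected, but it does not threaten the main ADA result. The effect is limited to the AZD7442 transient category and the titer summary and AE listing that use it, within a descriptive analysis.

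**What to change.** In SAP Section 4.2.1.2, replace the combination-level sentence with:

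> *AZD7442 is transiently positive if the participant is treatment-emergent ADA positive for AZD7442 and neither AZD8895 nor AZD1061 fulfils the persistently positive definition.*

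In the preceding bullet, changing *one of* to *at least one of* would remove the second ambiguity.

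Add a programming check that AZD7442 persistent plus transient equals AZD7442 treatment-emergent. Run it participant by participant, so that each treatment-emergent participant is in exactly one class, because the totals can agree by chance.

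If outputs already exist, compare the coded derivation with the corrected rule and record the clarification. The cost is one sentence and a short check, with no change to data collection or to the protocol.

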9.4.1.2 Antidrug Antibodies

The incidence of ADA to AZD7442 will be assessed and summarized by number and percentage of participants who are ADA positive. The ADA titer will be summarized with descriptive statistics.

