1.1 Objectives and Endpoints

Table 1: Objectives and Endpoints

Objective	Endpoint
Primary	
To evaluate the safety and tolerability of AZD7442	AEs, SAEs, and AESIs
To evaluate the immunogenicity of AZD7442	Incidence of ADA in serum
Secondary	
To evaluate the PK of AZD7442 in serum	
 • Serum AZD7442 concentrations • PK parameters
To determine anti-SARS-CoV-2 nAb levels in serum after administration of AZD7442	Changes from baseline in GMTs and GMFRs values in SARS-CoV-2 nAbs (wild-type assay or pseudo neutralization assay)
Exploratory	
To estimate the efficacy of AZD7442 for the prevention of COVID-19	
 • Incidence of SARS-CoV-2 RT-PCR-positive symptomatic illness • Incidence of participants who have a post-treatment response (negative at baseline to positive at any time post-baseline) for SARS-CoV-2 nucleocapsid antibodies

To estimate the efficacy of AZD7442 for the prevention of severe or critical symptomatic COVID-19	Incidence of SARS-CoV-2 RT-PCR-positive severe or critical symptomatic illness and COVID-19 deaths
To evaluate the PK of AZD7442 in nasal fluid	Nasal AZD7442 concentrations
To quantify SARS-CoV-2 viral loads in infected participants treated with AZD7442 (Illness Visits)	Viral genome copies in NP swabs at Illness Visits as determined by RT-PCR
To characterize resistance to AZD7442 (Illness Visits)	Genotypic analysis and biochemical and/or susceptibility analysis of SARS-CoV-2 variants to AZD7442
To assess additional immune responses in participants treated with AZD7442 (Illness Visits)	Other exploratory assays for humoral, mucosal, and cellular immune responses may be performed based upon emerging safety, efficacy, and pharmacodynamic data

Abbreviations: ADA = Antidrug antibody; AE = Adverse event; AESI = Adverse event of special interest; COVID-19 = Coronavirus disease 2019; GMT = Geometric mean titers; GMFR = Geometric mean fold rise; nAb = Neutralizing antibody; NP = Nasopharyngeal; PK = Pharmacokinetic; RT-PCR = Reverse transcriptase polymerase chain reaction; SAE = serious adverse event; SARS-CoV-2 = Severe acute respiratory syndrome-coronavirus 2.

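### ADA that first appears after dosing but never reaches 2 x MRD is labelled non-treatment-emergent and pooled with ADA present before the drug

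*SAP*

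**What the plan says.** The immunogenicity endpoint, one of two primary endpoints, is "Incidence of ADA in serum" (SAP 1.1; the Protocol has the same). Protocol 9.4.1.2 gives the analysis: "The incidence of ADA to AZD7442 will be assessed and summarized by number and percentage of participants who are ADA positive". It sets no titer floor and no baseline condition.

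SAP 4.2.1.1 makes an evaluable participant ADA positive if "a positive ADA result is available at any time, including baseline and all post-baseline measurements", again without a floor. SAP 4.2.1.2 then builds the categories:

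- Positive at any visit. The SAP calls this percentage ADA prevalence.
- Treatment-induced. The entry opens "Treatment-induced ADA positive (ADA negative at baseline and ADA positive at" and goes on to require one or more post-baseline assessments with a titer of at least 2 x MRD.
- Treatment-boosted, which needs a baseline titer that rises at least 4-fold.
- Treatment-emergent, meaning induced or boosted. The SAP calls this percentage ADA incidence.
- Two baseline-positive rows, one with and one without ADA detected after baseline.
- The residual class: "Non-treatment emergent ADA positive, defined as participants being ADA positive and not fulfilling the conditions for TE-ADA positive".

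SAP 4.2.1.3 summarizes PK concentrations and AEs, if the data allow, by "Treatment-emergent ADA positive, non-treatment emergent ADA positive, and ADA negative, and by treatment groups". SAP Section 2, on changes to protocol-planned analyses, deals only with the nAb set. SAP 4.2.1.4 plans no sensitivity analysis.

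**The concern.** The label says the opposite of what happened to these participants. Their ADA was absent before the drug, was confirmed after it, and is reported as not emerging on treatment. They share a class with people whose ADA predates dosing and was not boosted. They cannot be called persistently or transiently positive either, because both classes are limited to treatment-emergent participants.

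Two uses of the data are affected. The first is the row named ADA incidence, which takes its name from the endpoint but leaves this group out. SAP 4.2.1.3 describes its summary as covering participants in whom ADA became detectable, and this group meets that description. The second is the comparison of PK and AEs by ADA response, where the middle group mixes new and pre-existing ADA. Protocol 4.3 expects the study to show whether immunogenicity differs between 3-month and 6-month dosing, and new low-titer ADA is relevant to that question.

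**Working it through.** **The plan's own figure.** The only sizing figure is for AEs (SAP 1.3): 1 - 0.97^100 = 0.952, which reproduces the stated 95%. The documents give no numerical ADA rate.

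**Classification.** Applying the SAP 4.2.1.2 rules to one mAb component, with titers in multiples of MRD:

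| Baseline | Highest post-baseline | ADA positive | Induced | Boosted | In SAP incidence | Residual class |
|---|---|---|---|---|---|---|
| negative | 1 | yes | no | no | **no** | **yes** |
| negative | 2 | yes | yes | no | yes | no |
| 1 | not detected | yes | no | no | no | yes |
| 1 | 2 | yes | no | no | no | yes |
| 1 | 4 | yes | no | yes | yes | no |

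The first row is the group at issue. Boosting needs a baseline titer, so it cannot rescue a baseline-negative participant. Rows 3 and 4 are the pre-existing ADA with which the group is pooled.

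**Size.** Let r be the proportion of evaluable participants with new post-baseline ADA at any titer, and f the share of these that never reach 2 x MRD. The induced percentage is r(1 - f) with the floor and r without it, so the gap is r x f. Boosted participants are the same under both. Every r and f below is an assumption:

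| r | f = 0 | f = 10% | f = 25% | f = 50% | Gap (points) |
|---|---|---|---|---|---|
| 5% | 5.0% | 4.5% | 3.75% | 2.5% | 0 to 2.5 |
| 10% | 10% | 9% | 7.5% | 5% | 0 to 5 |
| 20% | 20% | 18% | 15% | 10% | 0 to 10 |

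The f = 0 column applies if no confirmed positive sample titers below 2 x MRD. The documents give neither the MRD nor the lowest reportable titer, so that case cannot be ruled out.

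**Can the count be recovered from planned rows?** For one mAb, yes:

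new low-titer ADA = (positive at any visit) - (treatment-induced) - (positive at baseline and after) - (positive at baseline only).

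This held in all 20 patterns tested (baseline 0, 1, 2, 4 by post-baseline 0, 1, 2, 4, 8). It was not shown for combined AZD7442. A participant positive at baseline to one mAb and newly low-titer positive to the other would be hidden there, and the SAP does not say how the two baseline-positive rows are formed for the combination. In the PK and AE summaries only three groups appear, so there is nothing to subtract.

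**The case against.** The strongest reply is that nothing promised is missing. The Protocol asks for ADA incidence to be "summarized by number and percentage of participants who are ADA positive", and the SAP's any-visit row gives exactly that with no floor, under the name prevalence. The sample-size rationale also speaks of ADA prevalence. The 2 x MRD floor is pre-specified, recurs in the persistent and transient definitions, and applies equally to both arms. By-visit results and titers, maximum titer by category and participant-level listings are all planned. For AZD7442, a low titer to one mAb does not remove a participant who is treatment-emergent to the other. The PK and AE summaries by ADA response are descriptive and conditional on the data.

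All of that stands. It defeats the stronger inference a reader might draw, that the SAP understates a primary endpoint or has replaced it without saying so. The treatment-emergent row is correct for its own definition, the Protocol's measure is still reported, and the affected group may be empty. Some low-titer positives may also be false positives, so a count without the floor is not automatically nearer the truth.

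It does not answer the labelling. New ADA still sits under a name that denies it is new, no row shows it, and the three-group summaries cannot separate it from pre-existing ADA.

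**Conclusion.** The point holds as a matter of classification and labelling. It follows directly from SAP 4.2.1.1 and 4.2.1.2 and needs no numerical assumption. Compared with a threshold-free count of new ADA, the row named ADA incidence can only be equal or lower. The gap, r x f, is unknown from the documents. It is 0 to 5 points if r is 10% and f lies between 0 and 50%, and zero if no confirmed positive falls below 2 x MRD.

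No hypothesis is tested (Protocol 9.1, SAP 3.3.4), so no error rate, power or decision rule is involved, and being one of two primary endpoints carries no testing consequence. The practical harm is confined to how the incidence row is read and to the mixed middle group in the PK and AE summaries. The change is worth making because it is cheap and uses data already collected.

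**What to change.** Keep the 2 x MRD definition of treatment-induced ADA, and make these changes:

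1. In SAP 4.2.1.2, add a category for participants negative at baseline and positive after it with a maximum titer below 2 x MRD, reported for AZD8895, AZD1061 and AZD7442. State the rule for AZD7442, for example: not treatment-emergent to either mAb, and in the new category for at least one.
2. Show treatment-emergent incidence with and without the floor, side by side.
3. In the PK and AE summaries of SAP 4.2.1.3, put this group on its own line and keep the non-treatment-emergent label for baseline-positive participants who were not boosted.
4. Note the floor in SAP Section 2, and say which row answers the Protocol's wording and which the SAP calls incidence.

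The cost is one extra row per ADA table and one extra group in the PK and AE summaries. No new samples or assays are needed. The added row may contain some low-titer false positives, and the figure without the floor may be higher for that reason. A footnote can say so.
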